4.3.4. Data collection

Data and samples will be collected as described below. The *2D-BioPAD baseline visit* refers to data and samples collection for all 300 recruited patients. The *2D-BioPAD feasibility test-run* refers to additional data and samples collection for the first 30 patients recruited during Step 1. A total of up to 30 ml blood will be drawn per patient for all samples together (including the additional Step 1 sampling).

²⁴ Huber H, Ashton NJ, Schieren A, Montoliu-Gaya L, Molfetta GD, Brum WS, Lantero-Rodriguez J, Grötschel L, Stoffel-Wagner B, Coenen M, Weinhold L, Schmid M, Blennow K, Stehle P, Zetterberg H, Simon MC. Levels of Alzheimer's disease blood biomarkers are altered after food intake-A pilot intervention study in healthy adults. *Alzheimers Dement*. 2023 Dec;19(12):5531-5540. doi: 10.1002/alz.13163

The *follow-up* is potentially applicable to all 300 recruited patients, but the primary focus is on patients whose diagnosis is unclear at baseline and have a follow-up visit scheduled as per centre-specific standard procedures.

4.3.4.1. At the 2D-BioPAD baseline visit

Data (including existing data from centre-specific standard assessments) will be collected for use in this study only after the informed consent form has been signed.

Table 6. Data collected from patients

Existing data from centre-specific standard assessments
Cognitive status 
 • Control / no dementia disease / subjective cognitive complaints • MCI • Dementia type • Date of diagnosis
Demographics, e.g.: 
 • Age • Gender (as recorded in medical records) • Years of formal education • Civil status • Work status
Family history of AD/other dementias in first degree relatives
#Neuropsychological test results and function in activities of daily living according to the standard diagnostic protocol of the respective centre.
Medical history (ICD-10 codes)
Current medication (ATC codes)
Markers of kidney and liver function, e.g., creatinine (with the Chronic Kidney Disease Epidemiology Collaboration CKD-EPI equation used to estimate glomerular filtrate rate, eGFR) and ASAT; other centre-specific markers may include e.g., urea, ALAT, GGT, CPK)
Systolic and diastolic blood pressure
Height and weight, BMI
Semiquantitative/visual brain MRI ratings if available (e.g., MTA, Fazekas)
*Results of CSF biomarker analysis according to the centre-specific standard protocol (e.g., A β 40, A β 42, total tau, ptau-181) if available
Results of genetic testing (APOE genotype) if available
Amyloid-PET visual ratings (e.g., positive/negative) if available
Visual readings of FDG-PET scans if available
New data
Blood sample for measurement of plasma AD biomarkers (A β 40, A β 42 and the A β 42/40 ratio, p-tau217, NfL, GFAP) using benchmarking equipment **
Blood sample for measurement of plasma AD biomarkers using the 2D-BioPAD diagnostic aid
Questionnaire including feedback about experience with 2D-BioPAD diagnostic aid
Self-reported lifestyle questionnaire

A minimum set of tests conducted at all study centres should include:

- Mini Mental State Examination (MMSE)
- Consortium to Establish a Registry for Alzheimer's Disease (CERAD)
- Alzheimer's Disease Cooperative Study Activities of Daily Living inventory (ADCS-ADL)
- Montgomery-Asberg Depression Rating Scale (MADRS)

* State-of-the-art CSF biomarkers as described in section 4.1.4.1. To reduce patient burden, the 2D-BioPAD prospective study will use CSF biomarker values where available from standard assessment procedures at the clinical study centres.

** Benchmarking equipment for plasma AD biomarkers as described in Section 4.1.4. All plasma samples for all patients will be analysed at the UEF Brain Research Unit biomarker laboratory.

Data collected from HCPs will include:

- Age
- Gender (self-reported)
- HCP group (e.g., nurse, physician)
- Clinical specialty
- Years and degree of experience (e.g., resident, specialist)
- Questionnaire including feedback about experience with the diagnostic aid and biomarker results on the 2D-BioPAD digital interface, acceptability, trust and satisfaction (short questions with Likert-scale answers to be answered via the digital interface after blood sampling and visualisation of plasma biomarker results for each patient; longer questionnaire to be answered e.g., 3-4 times during the study after the HCP has conducted blood sampling and visualisation of plasma biomarker results for multiple patients).

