4.3.3.1. Step 1: feasibility test-run

In Step 1, a small-scale feasibility test run will be performed with the first 30 recruited patients (10 per study centre) to refine the procedure for using the diagnostic aid by identifying constraints, limitations, and potential improvements. To assess the potential impact of fasting versus non-fasting state, and time of day, blood sampling for each patient will be done **in the morning** (one fasting sample before 09:00, and one sample about one hour after breakfast on-site) **and in the afternoon** (non-fasting after 13:00 on the same day). This is based on recent studies indicating that AD blood biomarker levels may be modified by food intake, and also showing significant changes over a 3-hour interval in the fasting control group²⁴.

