4.3.4.2. At the 2D-BioPAD feasibility test-run

This applies only to the first 30 recruited patients, and the additional plasma sampling in the feasibility test run.

Data collected from patients:

- Additional blood samples for measurement of plasma AD biomarkers using the 2D-BioPAD diagnostic aid, and using benchmarking equipment, as per schedule described in section 4.3.3.1

Data collected from HCPs:

- Questionnaire including feedback about experience with the diagnostic aid and biomarker results on the 2D-BioPAD digital interface (short questions with Likert-scale answers to be answered via the digital interface after blood sampling and visualisation of plasma biomarker results for each patient; optional free form written notes/comments).

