4.3.5.3. Missing data

Missing data in the 2D-BioPAD prospective study is defined as:

- Missing blood samples and/or related AD biomarkers measured using the 2D-BioPAD diagnostic aid and/or benchmarking equipment. The three study centres have extensive experience with blood sampling for clinical research studies, which reduces the risk of sampling failures. A sufficient amount of blood will be collected to allow completion of AD blood biomarker measurements in case of technical issues with some of the samples.
- Missing answers from patients in self-reported questionnaires. Completion will be ensured by HCPs checking the questionnaires during the 2D-BioPAD baseline visit.
- Missing answers from HCPs in questionnaires. Technical solutions will be applied in the 2D-BioPAD digital interface to design the questionnaires in a way that reduces the potential to skip or miss questions.

Most data collected from patients in the 2D-BioPAD clinical pilot study will be data generated during the standard assessment procedures at each study centre. Since these data reflect real-world clinical routines, missing assessments will not be treated as missing data. A pre-defined core set of assessments will be conducted in the same way across all centres (section 4.3.4).

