4.4.2. Prospective study outcomes

Table 9. Overview of the prospective study outcomes

Outcome type	Description
Primary	
 Sensitivity, specificity, positive and negative predictive values of plasma biomarkers measured with the 2D-BioPAD prototype versus benchmarking equipment (same as above) for identifying AD diagnosis established as per centre-specific standard procedures. Overall experience of HCPs with the 2D-BioPAD diagnostic aid Overall experience of patients with the 2D-BioPAD diagnostic aid
Secondary	
 Comparison of plasma biomarker values between 2D-BioPAD prototype and benchmarking equipment, considering the potential impact of other parameters, e.g., demographics, comorbidities, disease stage Sensitivity, specificity, positive and negative predictive values of plasma biomarkers measured with the 2D-BioPAD prototype for identifying AD-related pathology (e.g., β-amyloid, tau), as indicated by either plasma biomarkers from benchmarking equipment or, where available, CSF biomarkers measured during routine assessments at the clinical study centres using state-of-the-art equipment. Investigating plasma biomarkers measured with 2D-BioPAD prototype versus benchmarking equipment in relation to cognitive, clinical and other data Assess if user experience (HCPs and patients) with the 2D-BioPAD diagnostic aid varies by country, clinical specialty, and/or years of experience Assess if the information provided to HCPs via the digital interface of the 2D-BioPAD diagnostic aid is understandable and relevant Collect feedback for diagnostic aid improvement from HCPs and patients

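### The short per-patient HCP rating follows a displayed result and runs through the device's own interface, so the per-test part of a primary outcome would be selected towards tests that worked

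*Protocol*

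**What the plan says.** Table 9 (Protocol 4.4.2) lists as a primary outcome of the prospective study "Overall experience of HCPs with the 2D-BioPAD diagnostic aid". It names no instrument and no summary measure.

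Section 4.3.4.1 describes two HCP instruments. The first is a set of short Likert questions, "to be answered via the digital interface after blood sampling and visualisation of plasma biomarker results for each patient". The second is a "longer questionnaire to be answered e.g., 3-4 times during the study after the HCP has conducted blood sampling" and viewed results for several patients. For the 30 patients of Step 1, section 4.3.4.2 keeps the timing and route of the short form and adds free text: "to be answered via the digital interface after blood sampling and visualisation of plasma biomarker results for each patient; optional free form written notes/comments".

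Section 4.3.5.3 lists "Missing answers from HCPs in questionnaires" as a category of missing data. Its remedy is a form whose items are hard to leave blank: "Technical solutions will be applied in the 2D-BioPAD digital interface to design the questionnaires in a way that reduces the potential to skip or miss". The same section provides for enough blood to complete the biomarker measurements if some samples meet technical problems. Section 4.3.2.1 foresees technical problems and describes in-app troubleshooting and direct contact with technical support. Section 4.4.3 says that user experience will be analysed mainly descriptively.

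**The concern.** The timing of the short form fixes which tests get rated. A test that is abandoned, or that never produces a readable result, does not reach the step after which the form is answered. If the app or its connection is what failed, the form may not be available either. The safeguard in 4.3.5.3 acts on questions skipped inside a form that has opened. It does not create a form for a test that ended early.

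These are plausibly the uses that an HCP would rate worst, so the ratings would be absent for a reason related to what they measure. Step 1 has the same timing, although its purpose is "to refine the procedure for using the diagnostic aid by identifying constraints, limitations, and potential improvements". Table 9 also has a secondary outcome on whether user experience varies by country. If the share of tests without a result differed between centres, ratings restricted to successful tests would not be comparable across them.

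This is a matter of data capture. A rating that was never collected cannot be recovered by an analysis plan.

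**Working it through.** **The plan's own figures.** The protocol states no device failure rate, no expected rating and no precision target for HCP experience, so there is no figure to reproduce. The counts agree: 10 patients × 3 centres = 30 in Step 1, and 30 + 270 = 300 in total.

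**Inputs.**
- Number of patients: 300 (4.3.3). Step 1 has three samplings per patient, so sampling occasions are 30 × 3 + 270 = 360. The bias below does not depend on which count is used.
- f, the share of tests with no result at the first run: not in the protocol; assumed 10% and 20%.
- g, the gap in mean rating between tests with and without a result, on an assumed 5-point scale: not in the protocol; assumed 2 points.
- Repeat run: 4.3.5.3 provides spare blood but does not say how often a repeat will be run or succeed. The two cases taken are no repeat, and one repeat that fails independently with the same probability f.

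**Formula.** Let m be the mean rating when a result is shown, and q the share of tests that never show one. The mean over all tests is (1 − q)·m + q·(m − g) = m − q·g. The observed mean is m, so the bias is q·g. Without a repeat q = f; with one independent repeat q = f².

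| f | g | Repeat | q | Unrated of 300 | Bias (points) |
|---|---|---|---|---|---|
| 10% | 2 | none | 0.10 | 30 | +0.20 |
| 20% | 2 | none | 0.20 | 60 | +0.40 |
| 10% | 2 | one, independent | 0.01 | 3 | +0.02 |
| 20% | 2 | one, independent | 0.04 | 12 | +0.08 |

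If a repeat tends to fail for the same reason as the first run, q lies between f² and f, and the bias lies between the matching rows.

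**Wider range.** At f = 2% and g = 0.5, the bias is 0.02 × 0.5 = +0.01 without a repeat. At f = 30% and g = 3, it is 0.30 × 3 = +0.90 without a repeat and 0.09 × 3 = +0.27 with one.

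**As a proportion satisfied.** Assume 85% satisfied after a displayed result and 20% after none, a gap of 65 percentage points. Without a repeat, the overstatement is 0.10 × 65 = 6.5 points at f = 10% and 0.20 × 65 = 13 points at f = 20%. With one independent repeat it is 0.01 × 65 = 0.65 and 0.04 × 65 = 2.6 points.

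**After the fix.** If every attempted test is rated, q = 0 and this bias is zero.

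**The case against.** The timing can be read as a description of the normal workflow. The protocol sets no conditional rule and nowhere forbids an HCP from rating a failed test. Some of the questions concern the displayed results, so placing them after the display is natural.

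The primary outcome is also wider than the short form. The longer questionnaire is put to the HCP after use in several patients, so failures among those patients can be reported there. Step 1 has "optional free form written notes/comments". Section 4.3.5.4 asks for an explanation in the case report form when required data are omitted. If testing moves to a local laboratory, 4.3.5.1 separates the questions on sampling and testing from those on results and interface. Spare blood will rescue some failed first runs, and those tests are then rated. The analysis is mainly descriptive, in a pilot with at least 6 HCPs, so no error rate, margin or power depends on the rating.

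Most of this stands, and it limits the point to the per-test component. It does not remove it. A questionnaire answered about three or four times, placed after results have been viewed for several patients, relies on recall and gives no rating for a particular test. The Step 1 notes are optional and cover only the first 30 patients. An explanation for a missing rating is not a rating. A descriptive summary has no protection against selection in what it describes.

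A reader might infer more: that failed tests vanish from the primary HCP outcome altogether, or that the reported experience is certainly inflated. The protocol supports neither. Table 9 ties the outcome to no single instrument, other channels exist, and inflation needs both a non-zero final failure rate and lower ratings after failure.

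**Conclusion.** The point holds for the per-test ratings. They are timed after a displayed result and entered in the interface of the product being rated, with no stated route for a test that never displays one. Followed literally, that component of a primary outcome is selected towards successful tests. The direction is upward if tests without a result occur and are rated lower, which is plausible for an early prototype but is not established by the protocol.

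The size depends mainly on how many failed runs a repeat rescues. On the assumed inputs it ranges from negligible with an effective repeat to several tenths of a point without one. Acting is justified because the affected data cannot be obtained later and the correction costs very little.

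**What to change.** In 4.3.4.1 and 4.3.4.2, change the timing so that the short form is answered after every attempted 2D-BioPAD test, whether or not a result is displayed. Items about the result display are marked not applicable when there is none.

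- Add one test-status field: result at first run, result after repeat, no result.
- Provide the same short form in REDCap, which 4.3.5.4 already foresees, or on paper, for when the digital interface is unavailable.
- Report the per-test ratings over all attempted tests, together with the number that gave no result. Ratings after a displayed result can be shown as a supplement.

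The cost is a wording change in two sections, one extra field and a back-up copy of a short form. No extra patients, visits or blood are needed. The small downside is that HCPs answer a few questions after a failed test as well.

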4.3.4.2. At the 2D-BioPAD feasibility test-run

This applies only to the first 30 recruited patients, and the additional plasma sampling in the feasibility test run.

Data collected from patients:

- Additional blood samples for measurement of plasma AD biomarkers using the 2D-BioPAD diagnostic aid, and using benchmarking equipment, as per schedule described in section 4.3.3.1

Data collected from HCPs:

- Questionnaire including feedback about experience with the diagnostic aid and biomarker results on the 2D-BioPAD digital interface (short questions with Likert-scale answers to be answered via the digital interface after blood sampling and visualisation of plasma biomarker results for each patient; optional free form written notes/comments).

4.3.4.3. At follow-up

For all 300 patients, up to 1 year follow-up after baseline will be included if the diagnosis is unclear at baseline and follow-up is scheduled as per centre-specific standard procedures. The following patient-related data will be collected:

- Cognitive status
 - Control / no dementia disease / subjective cognitive complaints
 - MCI
 - Dementia type
- Date of diagnosis

4.3.5. Risk analysis

4.3.5.1. Development of the 2D-BioPAD diagnostic aid

Potential clinical pilot study risks related to the 2D-BioPAD diagnostic aid development and mitigation strategies are listed below.

- **Prototype functionality limitations requiring more extensive pre-processing of samples at the clinical study centres** (risk: moderate | impact: low)

Impact: A potential need for more extensive pre-processing of samples would not affect the clinical pilot study at UEF, i.e. the UEF biomarker laboratory can handle additional pre-processing on-site. Benchmarking at UEF for samples from all study centres would also not be affected. However, if the 2D-BioPAD prototype requires more extensive sample pre-processing, the GAADR and ZI study centres may need to rely on the local laboratories that they already use for routine blood sampling and testing. This would change the prototype testing setup from *direct* HCP-patient testing with immediate results on-site to the currently used *indirect* routine setup, i.e. laboratory-based sampling/measurement with results delivered separately to HCPs, who then inform patients as needed.

Mitigation: Because this is a clinical *pilot* study, the design has sufficient adjustment room for covering two different prototype testing setups (direct and indirect). In the indirect setup, the HCPs feedback questions would be separated into two parts, one for the laboratory (sampling/testing) and one for the HCPs (results/digital interface). The patient feedback questionnaire can be easily adapted because patients are not informed about not yet validated biomarker results. Additional feedback would allow comparisons between direct and indirect setups. Comparison with benchmarking equipment would be the same. GAADR and ZI are currently assessing the details of a potential shift from direct to indirect prototype testing setup at these study centres.

- **Number of 2D-BioPAD diagnostic aids ready-to-use by the clinical study centres lower than expected** (risk: low | impact: moderate)

Impact: With a lower number of diagnostic aids, recruitment would be expected to take longer time.

Mitigation: The total number of 300 patients can still be recruited because the current timeline (section 4.5) accounts for 1-year follow-up in cases where the diagnosis is initially not fully clear. The recruitment duration could thus be extended, and selection criteria adjusted to limit or exclude unclear cases, i.e., shift towards a more typical case-control study design, which is fully appropriate in a pilot study.

- **Significant delay in delivery of a prototype ready-to-use by the clinical study centres** (risk: low | impact: moderate)

Impact: Significantly delayed start of recruitment, and/or potential shift from prototype testing in real-life clinical environments to laboratory-only testing.

Mitigation: As above for delays in recruitment. In case of major delays estimated to significantly affect the total sample size that is feasible to recruit before the end of the project, the clinical pilot study design will be adapted, with more emphasis on plasma samples analysis in a laboratory/technical environment. I.e. recruitment can start as planned, including collection of new plasma samples, but prototype-based biomarkers will be measured by the technical partners in their laboratory environment (benchmarking at UEF laboratory would not change). The HCPs and patient feedback questionnaires would be replaced with e.g. usability and user experience assessments, focus groups, and/or workshops based on prototype-related scenarios identified by technical partners as most useful for further prototype development. A smaller real-life environment testing could still be included when at least one ready-to-use prototype becomes available.

4.3.5.2. Clinical pilot study sample size considerations

This is a clinical pilot study, i.e., the first study to evaluate and validate AD blood biomarkers measured using the newly developed 2D-BioPAD diagnostic aid in human plasma samples and in clinical environments in three countries. Sample size considerations for the prospective study are summarized in Table 6.

Table 7. Sample size for the prospective study

Study	Sample size	Rationale
Prospective, feasibility	30 patients 3 plasma samples/patient	10 patients per study centre appropriate for an initial feasibility assessment when shifting from a laboratory to a clinical environment. Repeated blood sampling allows initial assessment of use conditions in a clinical environment.
Prospective, full study	300 patients 1 plasma sample/patient	Sample size is in line with recent pilot studies of AD blood biomarkers validating new assessment methods for AD blood biomarkers ²⁵ or studies comparing different assessment methods ^{26,27,28} .
Prospective, feasibility & full study	At least 6 HCPs (2/study centre)	Sample size allows detailed initial feedback from several medical specialties and HCP categories with various degrees of experience.

4.3.5.3. Missing data

Missing data in the 2D-BioPAD prospective study is defined as:

- Missing blood samples and/or related AD biomarkers measured using the 2D-BioPAD diagnostic aid and/or benchmarking equipment. The three study centres have extensive experience with blood sampling for clinical research studies, which reduces the risk of sampling failures. A sufficient amount of blood will be collected to allow completion of AD blood biomarker measurements in case of technical issues with some of the samples.
- Missing answers from patients in self-reported questionnaires. Completion will be ensured by HCPs checking the questionnaires during the 2D-BioPAD baseline visit.
- Missing answers from HCPs in questionnaires. Technical solutions will be applied in the 2D-BioPAD digital interface to design the questionnaires in a way that reduces the potential to skip or miss questions.

Most data collected from patients in the 2D-BioPAD clinical pilot study will be data generated during the standard assessment procedures at each study centre. Since these data reflect real-world clinical routines, missing assessments will not be treated as missing data. A pre-defined core set of assessments will be conducted in the same way across all centres (section 4.3.4).

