4.3.1. Selection criteria

Table 5. Inclusion and exclusion criteria for the prospective study

Inclusion criteria	
Patients	
 • Age 50 years or older • Subjective cognitive complaints, MCI or dementia diagnosis, as per centre-specific standard assessment procedures • Ongoing assessment after first referral to the clinical study centre, or diagnostic procedures completed \leq3 months before the first 2D-BioPAD study visit • Ability to provide written informed consent
HCPs	
 • 18 years or older • Certified HCP (e.g., nurse, physician) • Actively involved in the centre-specific assessment process for dementia-related diseases
Exclusion criteria	
Patients	
 • Any health conditions that substantially affect communication and/or ability to participate in study procedures, as judged by the study nurse or physician • Impaired capacity to consent as per centre-specific standard assessment

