4.3.2. Overall study design

This is a **multicentre prospective observational study**. HCPs will use the 2D-BioPAD diagnostic aid to measure AD blood biomarkers in individuals referred to the three study centres for assessment of suspected AD/dementia disease. 2D-BioPAD baseline visit activities will be conducted only after the informed consent form has been signed. The overall study design is summarised in Figure 4.

The 2D-BioPAD baseline visit will be conducted after centre-specific standard assessment procedures are completed and a diagnosis and treatment/care plan have been decided according to standard clinic procedures. The 2D-BioPAD baseline visit can be a separate visit or can be conducted at the end of an already scheduled standard clinic visit, depending on patient preference and study centre logistics. The aim is to reduce burden for patients and limit interference with routine clinical activities.

As validation of the biomarker measures from the 2D-BioPAD diagnostic aid will be done as part of this study, these biomarker results will not be used for diagnosis or to guide treatment plans. HCPs participating in the 2D-BioPAD clinical pilot study who are directly involved in the standard diagnostic work-up and decision-making for patients tested with the 2D-BioPAD diagnostic aid must not have access to the biomarker results before the diagnosis and treatment/care plan are decided (See also Section 4.1.5.1 Ethical aspects).

[figure not shown]

Figure 4. 2D-BioPAD clinical pilot study design for the prospective stage

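### The HCP completeness check covers the patients' device-feedback form, the source of a primary outcome, so device-operating HCPs may see the ratings at the visit, with a risk of favourable bias.

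*Protocol*

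**What the plan says.** Table 9 in Protocol section 4.4.2 lists "Overall experience of patients with the 2D-BioPAD diagnostic aid" among the primary outcomes of the prospective study. Table 6 in section 4.3.4.1 names the source among the new data collected at baseline: "Questionnaire including feedback about experience with 2D-BioPAD diagnostic aid". The other new patient form in that table is the self-reported lifestyle questionnaire.

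Section 4.3.5.3 counts "Missing answers from patients in self-reported questionnaires" as missing data and gives one preventive measure: "Completion will be ensured by HCPs checking the questionnaires during the 2D-BioPAD baseline visit". The measure applies to patient questionnaires in general and does not distinguish the two forms. In the same section, blanks in the HCPs' own questionnaires are to be prevented by how the form is built into the digital interface.

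On who the HCPs are, section 4.3.2 says "HCPs will use the 2D-BioPAD diagnostic aid to measure AD blood biomarkers in individuals referred to the three study centres". Table 5 requires them to be "Actively involved in the centre-specific assessment process for dementia-related diseases". Section 4.3 sets a minimum of two per centre. Table 9 also makes "Overall experience of HCPs with the 2D-BioPAD diagnostic aid" a primary outcome.

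**The concern.** Checking a form for blanks before the patient leaves is ordinary practice when the form records facts such as lifestyle. It is less neutral when the form asks for a judgement on a procedure that the checker, or the checker's close colleague, has just carried out. A patient who knows or expects that this person will handle the form may soften criticism.

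What is at stake is the credibility of a primary outcome, and of primary objective (ii) in section 3.2, which names acceptability, trust and satisfaction. The weakness lies in how the answers are collected, so a later analysis plan could not remove it. It would also work against the pilot's purpose, since section 2 says pilot studies help to identify changes that a device or its procedures may need.

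**Working it through.** The protocol gives no target, threshold, test or precision for patient experience, so there is no stated figure to reproduce. The check is mainly a reading of the sections side by side, with one calculation for scale.

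**Step 1: does the check reach the feedback form?** Section 4.3.5.3 refers to patients' self-reported questionnaires and to the baseline visit. Table 6 places both the feedback form and the lifestyle questionnaire at that visit. No exemption is stated, so on the text as written the check covers the feedback form.

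**Step 2: could the checker have performed the test?** HCPs use the device (section 4.3.2) and HCPs check the forms (section 4.3.5.3). Nothing separates the two tasks. With the minimum of two HCPs at a centre, and the check done by study HCPs, the checker is either the operator or the only other study HCP there.

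**Step 3: is a safeguard stated?** The protocol mentions no sealed return, no electronic return that bypasses the HCP, no uninvolved checker and no rule limiting the check to blank items.

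**Step 4: could later data reveal the bias?** Section 4.3.4.3 lists only cognitive status and date of diagnosis at follow-up. No second patient rating under other conditions is planned. Comparisons by country (Table 9), or between direct and indirect testing if that contingency arises (section 4.3.5.1), might give a hint. They could also be distorted themselves, because whether the checker is the operator could differ between the groups compared.

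**Step 5: scale.** Inputs: n = 300 (Table 7); favourable share p is assumed, because the documents give none. The 95% half-width is 1.96 × √(p(1 − p)/n).

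| Assumed p | Calculation | Half-width | Equivalent number of patients (half-width × 300) |
|---|---|---|---|
| 50% | 1.96 × √(0.25/300) | 5.7 points | about 17 |
| 80% | 1.96 × √(0.16/300) | 4.5 points | about 14 |
| 90% | 1.96 × √(0.09/300) | 3.4 points | about 10 |

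The last column is the number of patients who would have to move from a non-favourable to a favourable answer for the bias to equal the sampling error. An assumed net shift of 5 points exceeds the half-width at p = 80% and 90% and falls just short at 50%. An assumed shift of 10 points exceeds it throughout. A larger sample would narrow the interval but leave the shift in place. The table shows how little movement would matter; it is not evidence that such movement will occur.

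**The case against.** The best defence is that the sentence describes a check for completeness and nothing more. The forms are self-reported, and the protocol does not say that HCPs supervise completion, read the answers for content or discuss them. A reader might infer that patients rate the test in front of the clinicians who care for them. The text does not support that. Table 5 requires involvement in the centre's assessment process, not in that patient's care, and section 4.3.2 implies that some participating HCPs may not be directly involved in a tested patient's work-up. In the indirect setup of section 4.3.5.1, a laboratory would do the sampling and measurement. This all stands, and the point is limited accordingly.

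Several features reduce the pressure on patients. "The 2D-BioPAD baseline visit will be conducted after centre-specific standard assessment procedures are completed" and, under the same section, the care plan has been decided by then, so a critical answer cannot alter it. Patients are not told their 2D-BioPAD results (section 4.1.5.1), and feedback for improvement is explicitly sought (Table 9). These features lessen the risk but do not remove it. Patients with an unclear diagnosis may be followed for up to a year under the centre's own procedures.

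It can also be said that section 4.3.5.4 leaves detailed instructions to the manual of operations, which could assign an uninvolved checker. It could, but the protocol itself names HCPs and the visit. Finally, section 4.4.3 describes the user-experience analysis as mainly descriptive, in a pilot with no success criterion for this outcome. That limits the consequence. A descriptive result is still affected by how its answers are gathered.

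**Conclusion.** The point holds as a moderate design weakness, not as an error or contradiction. The completeness check extends to the form behind a primary outcome, so HCPs who operate and themselves rate the device may see patients' ratings at the visit, and no safeguard is stated. This carries a risk of favourable bias.

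A reader might go further and conclude that ratings will be pushed upwards by a known amount. The documents do not support this: an upward direction is plausible, but nothing in them shows or sizes it. The comparison with sampling error rests on an assumed favourable share of 50% to 90% and an assumed shift of 5 to 10 points, in 300 patients who all return the form. The change is worth making because it is cheap and because no planned later patient rating could correct the result.

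**What to change.** In section 4.3.5.3, limit the HCP check to the lifestyle questionnaire and add a separate rule for the device-feedback form:

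- Blanks are prevented by electronic required-answer fields that include a 'prefer not to answer' option, on the same principle as already planned for the HCP questionnaires. Alternatively, the form is returned on paper in a sealed envelope bearing only the study code.
- HCPs do not see the completed form at the visit.
- If a patient needs help, an existing study team member who did not perform that patient's test gives it, and this is recorded.

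No new staff are needed, and section 4.3.5.4 has the data-collection forms ready only by M24. The change still has costs. There may be a few more blank items, particularly among cognitively impaired patients using paper. The electronic form needs set-up at three centres; section 4.3.5.4 names REDCap only as an example for entering CRF data and as already available at UEF, so its use by patients at every centre cannot be taken for granted. Two ethics committees have approved version 1 and the third review is in progress, so the committees would have to be notified if the change is judged substantial.
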